The theoretical framework is informed by Lazarus and Folkman's transactional model in which perception of stressful situations is a transactional process of the person's cognitive-emotional appraisal of a situation in relation to their perceived coping resources to address the situation.⁶⁹ Appraisal is posited to take place in two stages. In primary appraisal, the person evaluates the situation as being irrelevant, benign, or stressful to their well-being. Secondary appraisal pertains to the person's perceived coping skills to manage the situation. An iterative process takes place over time in which secondary appraisals feedback upon primary appraisals, modulating the degree of stress experienced.

Mindfulness training is hypothesized to impact secondary appraisal of asthma symptoms and related components of the experience. Figure 1 illustrates that in the primary appraisal the patient may not clearly distinguish between respiratory symptoms and related stressful thoughts and feelings, increasing the possibility of less accurate perception of respiratory symptoms. The increased alertness to physical sensations that derives from exercises such as the body scan and the resultant capacity to distinguish physical symptoms from the symptom-related thoughts and feelings, together with the non-reactivity that is cultivated, makes possible a secondary appraisal⁴⁵.

The resultant reappraisal may result in improved asthma control through one or more of several avenues: (1) The patient will more accurately discriminate between their asthma symptoms and their emotional reactions associated with the experience and so is more clinically accurate; (2) The more accurate perception of symptoms may lead patients to better adherence of their medications, especially with regard to slowly acting inhaled corticosteroids; (3) Patients will better know, in a more timely fashion, when to seek medical help to adjust their therapy; and (4) Better perceptual accuracy and a more discriminating, objective self-assessment of symptoms may make patients more aware of their asthma triggers and lead them to better avoid stimuli that worsen airway inflammation and bronchospasm.

Following a successful feasibility study, an exploratory pilot study⁷⁰ (R21AT002938; Multiple PIs: [name] and [name]; Co-Investigator: [name]; 2006-2009) recruited 84 patients from UMMHC primary care and pulmonary care clinics with mild, moderate or severe asthma who were randomized to MBSR or an

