described above (e.g., purple sheet, in clinic recruitment or via letter). We also will recruit via newspaper ads and on-line.

At Miriam this report will be generated via EPIC LifeChart, the site's electronic medical record system. Miriam will also reach out to pulmonary practices in the community for referral of asthma patients. The study coordinator/RA will be contacted by the doctors if a potential subject is scheduled to be seen. The doctor will present the study to the patient, and if interested, the patient will sign a permission to contact form and the RA will follow up via phone to discuss the study and screen for eligibility or will be seen by the RA in the clinic.

As in our prior studies, a HIPAA waiver authorization will be requested from our Institutional Review Board prior to obtaining the list of patients. Exclusion and inclusion criteria also will be included in this search. At the UMMS site only, each physician will receive a spreadsheet of their patients' names and asked to cross off anyone who s/he does not feel would be appropriate to participate in the study. At Miriam, providers will not review a spreadsheet; rather, the report generated by EPIC/LifeChart will be used as a mailing list. A form letter signed by the physician and the Principal Investigator, and containing a stamped envelope, will be sent to each patient inviting them to participate. The patient will be asked to indicate if s/he is: (1) interested in participating, or (2) not interested in participating. All patients responding with 1 will be called.

We will also be reaching out to Conquering Diseases, a database of individuals who are interested in participating in research studies at both UMMS and Miriam. They will provide us a list of patients who have asthma and are interested in participating in the study. The RA will then email or call those patients.

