6.2 Description of Evaluations and Schedule

Each of the study evaluations are described in the following table, together with time point at which they are administered.

Construct/Function	Measures	Evaluation Time Points			
		BL	6m	12m	18m
Primary Outcome Asthma Control	Asthma Control Questionnaire (ACQ) ³ is a validated 7-item multi-component measure that assesses the 5 asthma symptoms considered most important and most used by clinicians for evaluating asthma control, along with use of short-acting beta-agonist and FEV ₁ percent predicted. Patients recall their symptoms and short-acting beta-agonist use during the previous week; FEV ₁ is obtained from spirometry. Questions are scored on a 7-point scale (0=good control, 6=poor control), and the overall score (range 0-6) is the mean of the seven responses. Changes of 0.5 or greater in the score are considered important differences. ⁸⁵	■	■	■	■
Secondary Endpoints					
Symptoms, Symptom-free days	Asthma Control Diary ³ completed daily for 2 weeks at each assessment point provides daily asthma symptoms and the proportion of symptom-free days per week. For comparison to the ACQ results, diary information will be combined with lung function data in order to categorize the level of asthma control according to 2012 GINA guidelines, with the categorical variables being controlled, partly controlled, and uncontrolled.	■	■	■	■
Medication Use	Both controller and reliever medication use will be documented daily during the 2-week assessment period. In addition, controller medication	■	■	■	■

	dose and frequency of use will be obtained from electronic prescription data. Prescription fills will be identified through pharmacy claims data as described in prior studies. ⁸⁶ These data identified more than 99% of all inhaled corticosteroids (ICS) prescriptions filled by health plan members. ⁸⁷ Adherence is estimated as the number of days' supply for each fill divided by the total number of days between the present fill and the subsequent ICS fill. Periodic adherence estimates will be assessed and a final overall mean measure of adherence is then calculated based on the percentage of ICS adherence for each interval.				

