Confounding Effects	A Confounding Effects Inventory (CEI) developed in our pilot study documents common confounding effects experienced in the past 6 months that could impact asthma control. These include environmental confounders in the home (moved, changes in active or passive smoking, pets), workplace, and social environments; medical problems (sinus infections, upper and lower respiratory tract infections, other infections, gastroesophageal reflux disease, surgery, and new diagnosis or change in status of other cardiovascular or respiratory conditions); changes in asthma and other medications; and changes in health insurance coverage.	■	■	■	■
CAM Use for Asthma/Concomitant Interventions	Self-report of CAM treatments for asthma (e.g. acupuncture, homeopathy, herbal medicine, prayer, supplements, dietary restrictions) in the 6 months prior to each assessment.	■	■	■	■

6.2.1. Screening Evaluation: Upon obtaining verbal consent the RA will complete the eligibility screen which will include questions related to the eligibility criteria using a script and screening form to standardize this phase of enrollment. Criteria for eligibility (inclusion and exclusion criteria) are listed in sections 4.1 and 4.2. A 6-week range will be allowed prior to study entry during which all screening evaluations to determine eligibility will be completed.

6.2.2. Participant Consent, Study Enrolment, Baseline Assessment and Randomization: Eligible persons will attend an orientation session on the day of their clinic visit or, if the RA was not able to be at the clinic on the day of their visit, at the study offices at that site during which the site RA will explain in full detail the study goals and procedures so as to familiarize the patient with what to expect, and what is expected from their participation in both the interventions and the assessments. Subjects will be informed about all of the risks

described above and all aspects of the study, and emphasize that their participation is voluntary and that they may withdraw at any time by contacting the RA and/or the contact PI. Contact information for the RA and the PI, as well as the IRB (for complaints) is contained in the consent form.

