Secondary Outcomes: Analytic approaches for asthma-related QoL, respiratory interoceptive accuracy, lung function are generally similar to those for the two primary outcomes. To test the mediation effect of respiratory interoceptive accuracy (RIA) on asthma control, QoL, and medication use, we will first compare the difference in RIA by treatment arm. We will then use difference-to-difference approach to analyze the longitudinal associations of the changes in RIA from baseline to each follow-up time point with changes in ACQ, QoL and medication use from baseline to comparable follow-up time points.¹⁰¹⁻¹⁰³ Since we will have measures on three follow-ups, we will use linear mixed models where ACQ, QoL and medication use are treated as outcomes, RIA as the primary predictor, with and without an interaction term between RIA and MBSR indicator. These analyses will help answer whether MBSR intervention improved RIA, and whether between treatment differences in RIA would explain the observed differences in ACQ, QoL and medication use. We will compute incremental cost-effectiveness of MBSR compared with HLC as the difference in average health care costs per study participant over 18 months between MBSR and HLC, divided by the difference in average ACQ. As planned for another NIH-funded cost-effectiveness study (5R01AA009892-19), we will use the overlap between self-reported and administrative reimbursement data to estimate models of administratively estimated inpatient, outpatient, and medication services data as functions of the self-reported data. We will apply these models to all self-reported data to derive the 18-month health care costs of MBSR and HLC. We will calculate the cost of delivering the MBSR and HLC from the Brief Treatment Cost Analysis Tool (TCAT), a validated costing tool for counseling interventions.⁸⁹ Sensitivity analysis: ICER ratios will be computed between baseline and active comparator, with usual considerations of uncertainty evaluated in a probabilistic sensitivity analysis to determine the level to which our cost-effectiveness conclusions are robust.

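### The claims-based inhaled-steroid adherence ratio ignores all time after the last fill, so it does not register participants who stop refilling

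*Combined protocol and SAP*

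**What the plan says.** The Medication Use row of the table in section 6.2, under the secondary endpoints, takes prescription fills from pharmacy claims. Each ICS fill is scored as the supply dispensed, in days, "divided by the total number of days between the present fill and the subsequent ICS fill". It then says that "a final overall mean measure of adherence is then calculated based on the percentage of ICS adherence for each interval". Periodic estimates are mentioned, but without period boundaries.

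No section closes the interval after the last fill, sets an observation window, caps a ratio above 100%, or says how to score a participant with one fill or none.

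Section 9.6 uses medication use in the mediation analysis, where "QoL and medication use are treated as outcomes" alongside ACQ. It does not say whether this means the claims ratio, the diary record or the prescribed dose. Section 2.2 gives adherence a place in the causal account: "The more accurate perception of symptoms may lead patients to better adherence of their medications", with ICS singled out.

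**The concern.** The denominator exists only when another fill follows, so the ratio measures how punctually people refill while they are still refilling. It says nothing about whether they carry on. Someone who stops early can get the same score as someone who refills on time for 18 months.

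Three further features follow from the same definition:

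- An early refill scores above 100%.
- When days' supply is equal, a simple mean gives a long gap no more weight than a short one.
- A participant with one fill drops out of the measure.

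Section 2.2 proposes better ICS adherence as one route by which MBSR may work, and discusses reduced adherence as an adverse possibility to be ruled out. Stopping is the clearest form of non-adherence. If the arms differ in how many participants stop, this ratio will not show it. The mediation analysis inherits the problem if this is the variable modelled.

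**Working it through.** **Inputs.** From the documents: the ratio and averaging rule (section 6.2) and 18 months on study (Précis), taken as 547 days. Assumed, because the documents give no value: 30-day supply per fill, the refill gaps and the stop rates. The plan states no adherence figure to reproduce.

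**Rule as written.** Interval ratio = days' supply / (next fill date − present fill date); overall score = simple mean of the interval ratios. **Comparator.** Days covered by dispensed supply / 547.

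**Hand examples (30-day supply)**

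| Fill history | Written rule | Days covered |
|---|---|---|
| 7 monthly fills, then none | six intervals of 30/30: 100% | 210/547 = 38.4% |
| 4 monthly fills, then none | three intervals of 30/30: 100% | 120/547 = 21.9% |
| 2 fills, then none | one interval of 30/30: 100% | 60/547 = 11.0% |
| 1 fill, then none | no interval, no value | 30/547 = 5.5% |
| 7 monthly fills, 360-day gap, one fill at day 540 | (6 × 1 + 30/360)/7 = 86.9% | (210 + 7)/547 = 39.7% |
| Every 45 days throughout | 30/45 = 66.7% | (12 × 30 + 7)/547 = 67.1% |

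The last row matters: a steady late refiller is scored almost correctly. The error sits with participants who stop or have long gaps. A refill at day 25 scores 30/25 = 120%.

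The averaging bias is not always upward. A 90-day fill lasting 100 days plus a 30-day fill lasting 45 days averages (0.900 + 0.667)/2 = 78.3%, against (90 + 30)/(100 + 45) = 82.8% when weighted by time.

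**Simulation.** There were 20,000 participants per setting, followed for 547 days. Each fill is followed by permanent stopping with a fixed probability; otherwise the next fill comes after 30 days plus an exponentially distributed extra gap.

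| Mean extra gap | Stop probability per fill | Stopped by 18 months | Written ratio | Days covered | No value |
|---|---|---|---|---|---|
| 20 days | 0 | 0% | 67.3% | 61.6% | 0% |
| 20 days | 0.01 | 10.6% | 67.3% | 58.6% | 1.0% |
| 20 days | 0.031 | 30.1% | 67.4% | 52.8% | 3.0% |
| 20 days | 0.05 | 44.4% | 67.4% | 47.9% | 4.9% |
| 20 days | 0.10 | 69.7% | 67.4% | 38.0% | 9.8% |
| 5 days | 0 | 0% | 87.2% | 86.2% | – |
| 5 days | 0.01 | 14.7% | 87.2% | 80.3% | – |
| 5 days | 0.02 | 27.8% | 87.2% | 74.7% | – |

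The zero-stopping rows separate the two effects. With a 20-day mean gap, 67.3 − 61.6 = 5.7 points arise without any stopping, essentially from the unweighted mean over irregular gaps. Stopping then lowers covered days by 61.6 − 58.6 = 3.0 points at 10.6% stopping and 61.6 − 52.8 = 8.8 points at 30.1%. The written ratio records neither fall. An arm with 10.6% stopping and one with 30.1% differ by 67.4 − 67.3 = 0.1 point on the ratio and 58.6 − 52.8 = 5.8 points on covered days.

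Within the 10.6% setting, stoppers who have a value score 68.0% with 36.7% of days covered; the others score 67.2% with 61.6% covered.

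**The case against.** The strongest reply is about consequence. The plan sets out no between-arm test of this ratio. Medication use has no hypothesis of its own; it appears only within the mediation and cost-effectiveness hypotheses, and section 9.6 does not name the variable. Harm to the mediation result requires both that this ratio is the variable and that stopping is related to arm or to the mediator. This stands, and it keeps the point at secondary-endpoint level.

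Stopping is also not invisible to the trial. Controller use is recorded daily for two weeks at each assessment, medications are recorded at each visit, and the Confounding Effects Inventory asks about the past six months, including "changes in asthma and other medications; and changes in health insurance coverage". This stands too, but these are separate records. They do not correct the claims ratio, and no section says they will be combined with it.

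The periodic estimates might be made per six-month period. Many stoppers would then have no value in later periods: in the 20-day-gap simulation, about 78% to 86% of stoppers had no closed interval starting after day 365. That replaces an inflated score with missingness that depends on adherence itself, so it is no remedy.

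The prior study cited for identifying fills may contain a rule for the last interval. That cannot be checked here, and the protocol does not state one. The reference attached to the claims-completeness figure is listed as a validation of a decentering questionnaire, so it does not supply one.

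Finally, one could simply close the last interval at the end of follow-up. Under an unweighted mean that is not enough: seven monthly fills and then none gives (6 + 30/367)/7 = 86.9%, against 38.4% covered.

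**Conclusion.** The concern holds. Followed literally, the stated rule gives a participant who stops refilling the same score as one who refills on time throughout, and gives no value after a single fill. That follows from the definition and needs no assumption.

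The size in this trial is unknown. It depends on stop rates, days' supply and gap lengths that the documents do not give, and the higher simulated stop rates show the range only. At the lowest non-zero stop rates simulated, 11% and 15%, stopping lowers covered days by 3 points (20-day mean gap) and 86.2 − 80.3 = 5.9 points (5-day mean gap), with no visible change in the ratio.

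The claims-based part of the Medication Use endpoint is affected, and the mediation analysis too if it uses this variable. The ACQ primary outcome, the sample size and the ACQ-based cost-effectiveness ratio are not. The definition should be changed, but the trial's main conclusion does not depend on it.

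**What to change.** Replace the ratio with days covered by dispensed ICS supply divided by days in a fixed window, for each six-month interval and for the full 18 months. Specify that:

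- surplus from an early refill is carried forward, and the result is capped at 100%;
- days after the last supply runs out count as uncovered;
- participants with one or no fill are included;
- the denominator contains only days with confirmed pharmacy-claims coverage, so that lost insurance or no claims link is missing data and not non-adherence;
- a recorded prescriber discontinuation or switch is handled separately, for example in a sensitivity analysis;
- the medication-use variable in the mediation model is named.

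The coverage condition matters here. The completeness figure in section 6.2 refers to "prescriptions filled by health plan members", whereas section 4.3 says "We also will recruit via newspaper ads and on-line", so some participants may have no claims link.

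The present ratio can be kept as a description of refill timing.

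The cost is a changed definition on the same fill data, plus claims-coverage start and end dates for each participant, which the documents do not say are collected. Reported adherence will generally look lower, and participants without confirmed coverage will have no claims-based value.

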5.4 Adherence Assessment

To assess adherence to the interventions the number of MBSR and HLC classes attended will be documented by instructors delivering the MBSR and HLC classes. Completion of homework during intervention will be assessed by participants completing homework logs that will be collected each week. MBSR

participants will record number of minutes of homework they do each day using the homework logs⁶². HLC participants will record their completion of weekly assignments. During follow up, MBSR participants will estimate the usual minutes of mindfulness practice they have been doing each week in the interval since their last assessment. Instructors will not see the completed logs which participants will place in a locked box in the classroom and which will be collected by the RA.

[figure not shown]
Based on the average number of classes attended, and homework completed, in the pilot trial, a protocol deviation will be considered to have occurred when a participant has attended less than five of the nine classes, and not completed the homework for those classes. Because MBSR and HLC programs will be open to the community, not just consented participants, we will not have permission from all attendees and are unable to record these programs. Fidelity to MBSR protocol will be ensured through ongoing weekly supervision meetings currently conducted with UMass Center for Mindfulness MBSR instructors in which curriculum delivery is reviewed and potential threats to fidelity are discussed. MBSR instructors at the Miriam Hospital site will participate in these weekly supervision meetings in person or via Skype to ensure fidelity and standardization across the two sites. Fidelity to HLC protocol by HLC instructors and standardization at both UMMS and Miriam sites will be ensured through weekly supervisory meetings held by [name], in which curriculum delivery is reviewed and potential threats to fidelity are discussed.

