Quality of life	Asthma Quality of Life Questionnaire (AQoL) ⁴ has 32 items assessing impairment in 4 areas of function shown to be important to the QoL of adult patients with asthma (activity limitations, asthma symptoms, emotional function and environmental exposure). Overall QoL is computed by averaging scores on the 4 domains. Items assess the degree to which important activities have been limited by asthma during the last 2 weeks on a 7-point scale (1= maximal impairment, 7= no impairment). Shown to be valid, reliable and sufficiently sensitive to changes in asthma symptoms to capture the effects of an intervention in a clinical trial. ^{4,88} Changes in scores of 0.5 or above represent clinically meaningful improvement in QoL.	■	■	■	■
Respiratory Interoceptive Accuracy (RIA)	The Breath Perception Discrimination Test (BPDT) measures ability to detect small changes in resistive load. This test will be done in the Pulmonary Diagnostic Laboratory at each site and follow procedures outlined in [name] recent publication. ⁵⁹ The test begins with a brief training period to familiarize participants with 5 resistive load settings (including 4 Hans Rudolph very-low-threshold calibrated resistors and 1 blank (no resistance) condition). During the test period, the presentation of the resistor is announced at the onset of a new inspiration for the duration of one full breath cycle. At the conclusion of the breath cycle, participants pause for 5 normal breaths, then the next resistor in the block is presented. The test will be divided into 6 blocks during which there is a random presentation of each resistor so that participants carry out 30 ratings (6 for each condition) over the course of the test. Time to complete: 30 minutes.	■	■	■	■
Exacerbations and Health Care Utilization/Cost	Number of moderate and severe exacerbation, asthma-related regularly scheduled office visits, acute care visits, hospitalizations, emergency room visits, need for intubation or mechanical ventilation, and other costs during the prior 6 months at baseline, 6-, 12- and 18-month follow-up and associated clinic and hospital costs will be determined by two methods: self-report, and actual hospital and health system costs (direct and indirect) obtained from administrative reimbursement data. Brief Treatment Cost Analysis Tool (TCAT), a validated costing tool for counseling interventions, ⁸⁹ will be used to calculate cost of delivering MBSR and HLC.	■	■	■	■

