Perceived Stress	Perceived Stress Scale (PSS), ⁹⁴ a well-validated 10-item scale based upon the transactional model, ⁶⁹ measures degree to which situations in one's life over the past month are appraised as unpredictable, uncontrollable and overwhelming. A higher score indicates a greater degree of perceived stress, and lower scores are associated with better coping resources. ⁹⁵ Higher PSS scores have been associated with failure to make health-promoting behavior changes. ^{96, 97} Participation in MBSR has been associated with significant declines in PSS scores. ⁹⁸	■	■	■	■
Moderating/Process Variables					
Sociodemographic Variables	Age, gender, race/ethnicity, years with asthma diagnosis, number of years taking asthma medication, body mass index, education level, marital status, employment status.	■			
Medical and Psychiatric History	Focused medical history, comorbid medical conditions, medications, smoking status, physician and ER visits, hospitalizations, and focused psychiatric history	■	■	■	■
Adherence to MBSR and HLC Requirements	Number of MBSR and HLC classes attended will be documented by instructors delivering the MBSR and HLC classes. Completion of homework during intervention will be assessed by participants recording number of minutes of home practice they do each day using homework logs. ⁶² During follow up, MBSR participants will estimate the usual minutes of mindfulness practice they have been doing each week in the interval since their last assessment. Participants who attended four or fewer intervention classes will be asked their reasons for non-attendance		■	■	■
MBSR and HLC Fidelity	MBSR instructors at both sites will participate in the ongoing weekly supervision meetings conducted with UMass Center for Mindfulness MBSR instructors to ensure fidelity to MBSR protocol. HLC instructors at both UMMS and Miriam will have weekly supervisory meetings with [name] in which curriculum delivery is reviewed and potential threats to fidelity are discussed.				
Days of Work/School Missed	Self-report of number of days of work or school missed because of asthma in the 6 months prior to each assessment.	■	■	■	■
Triggers/Seasonal Variability	Self-report from list of 11 common asthma triggers (e.g. aspirin, cold air, infections etc.), and the months of the year their asthma is worse	■	■	■	■

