In case the unblinding is necessary, the process will be formally monitored and documented. The PI's will draft a request for permission to unblind the codes to NCCAM, IRB and the DSMB. With the permission, the PI's will work with the database manager to reveal the study arm codes to the individuals authorized by the PI's, DSMB, NCCAM and DSMB. Hand signed documents will be kept by the database manager, and copied to DSMB, IRB and NCCAM. Unblinded individuals will be excluded from first round of statistical analysis of the main outcomes.

6.2.4 Follow-up Visits: As described in Section 6.1, study follow-up visits will occur 6- months, 12- months, and 18-months post-baseline. Section 6.2 describes the assessments that will occur at each of these time-points. Study assessment visits indicated in Section 6.2 will occur within a 3-week period before and after the 6-, 12-, and 18-month timeframes.

6.2.5 Completion/Final Evaluation: The final evaluation will be conducted at the 18-month post-baseline assessment and will consist of the assessments listed in Section 6.2 for this visit. We do not foresee any reason for participants' early termination from the study. However, any participants who discontinue study intervention early will be invited to complete all study evaluations.

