9.5 Outcomes

9.5.1 Primary Outcome: The primary objective is to evaluate the effect of MBSR in improving asthma control as assessed by the Asthma Control Questionnaire. *Hypothesis: Asthma control as assessed by the Asthma Control Questionnaire³ will improve significantly more in MBSR than in HLC participants at 18 month follow-up.*

9.5.2 Secondary Outcomes:

1) Asthma-related QoL. *Hypothesis: Asthma-related QoL (AQoL)⁴ will improve more in MBSR than HLC participants from baseline to 18-month follow-up.*

2) Respiratory interoceptive accuracy and its mediating effect on asthma control, QoL, and medication use. *Hypotheses: MBSR will result in improved accuracy (Breath Perception Discrimination Test) at 6-, 12- and 18-months compared with HLC, and will be correlated with improved asthma control, QoL, and medication use.*

3) Lung function (change from baseline in 2-week average morning peak expiratory flow (PEF) and spirometry (Forced Expiratory Volume in 1 second (FEV₁)) at 6-, 12- and 18-months compared with HLC. *Hypotheses: There will be no deterioration, and possibly improvement, in lung function in MBSR participants from baseline to 6-, 12- and 18-months as measured by PEF and FEV₁ as compared with HLC.*

4) Cost-effectiveness in asthma control and management. *Hypothesis: MBSR will be associated with improved cost-effectiveness and improved cost-utility by 18 months as compared with HLC. This will be based on clinical outcomes (e.g., asthma control, QoL, medication use) as well as quality-adjusted life years.*

To conduct cost analysis, we will collect data on number of moderate and severe exacerbations, asthma-related regularly scheduled office visits, acute care visits, hospitalizations, emergency room visits, need for intubation or mechanical ventilation, and other costs during the prior 6 months at baseline, 6-, 12- and 18-month follow-up and associated clinic and hospital costs. The cost data will be determined by two methods: Self-report and actual hospital and health system costs (direct and indirect) obtained from administrative reimbursement data (see Letters of Support from fiscal offices). Brief Treatment Cost Analysis Tool (TCAT), a validated costing tool for counseling interventions,⁸⁹ will be used to calculate cost of delivering MBSR and HLC.

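### The fixed six-month recall for exacerbations, healthcare use and costs does not match visit intervals of 20 to 32 weeks, and it leaves about 26 weeks unasked when a participant misses a visit and returns

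*Combined protocol and SAP*

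**What the plan says.** The utilization and cost row of the Section 6.2 table asks about exacerbations, visits, admissions and "other costs during the prior 6 months at baseline, 6-, 12- and 18-month follow-up". Section 9.5.2 repeats the same period for the cost analysis: "other costs during the prior 6 months at baseline, 6-, 12- and 18-month follow-up and associated clinic and hospital costs".

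Section 6.2.4 sets the timing: "study follow-up visits will occur 6- months, 12- months, and 18-months post-baseline". It then adds the window: "Study assessment visits indicated in Section 6.2 will occur within a 3-week period before and after the 6-, 12-, and 18-month timeframes".

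Section 9.6 fits models of administrative cost on self-report where the two sources overlap, and continues: "We will apply these models to all self-reported data to derive the 18-month health care costs of MBSR and HLC". It also says that total cost should span the whole follow-up period, and it names prevention of exacerbations, unscheduled acute visits and emergency visits as key clinical endpoints of the cost analysis.

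The text does not link the start of the recall period to the previous visit, ask for event dates, or say what to do about gaps, overlaps or a missed visit. Other items are worded differently. Section 5.4 asks MBSR participants about mindfulness practice "each week in the interval since their last assessment", and the adverse-event question in Section 7.4 also runs from the last contact.

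**The concern.** A fixed look-back covers follow-up exactly once only if visits are exactly six months apart. With the permitted window they need not be. A longer interval leaves weeks that no form asks about. A shorter one lets the same admission or emergency visit be reported on two forms. If the 6-month visit is early, its recall takes in time before baseline that the baseline form has already covered.

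An intermittent missed visit has a larger effect. The participant comes back, could report what happened, and is asked only about the most recent six months. The skipped period then has to be imputed or weighted for, although it could have been observed.

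What is at stake is secondary objective 4 (18-month cost-effectiveness) and the exacerbation and acute-care counts behind it.

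**Working it through.** The plan gives no figure for recall coverage, so there is none to reproduce.

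**Inputs.** Recall of six months, taken as 26 weeks (Sections 6.2 and 9.5.2). Follow-up visits at 26 + a, 52 + b and 78 + c weeks after baseline, with a, b and c each between −3 and +3 (Section 6.2.4).

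**Visit intervals.**
- Baseline to first follow-up: 26 + a = 23 to 29 weeks.
- First to second, and second to third: 26 + (b − a) and 26 + (c − b), each 20 to 32 weeks.

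**Mismatch per interval** (interval minus 26).
- First interval: up to 3 weeks unasked, or up to 3 weeks before baseline.
- Each later interval: up to 6 weeks unasked, or up to 6 weeks covered twice.

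**Average mismatch, assuming independent visit times uniform over the window.** The mean of the positive part of a is 3/4 = 0.75. The mean of the positive part of b − a is 1.0, and likewise for c − b.
- Unasked: 0.75 + 1 + 1 = 2.75 weeks, about 2.8 (3.5% of 78).
- Double counted within follow-up: 1 + 1 = 2.0 weeks.
- Before baseline: 0.75 weeks.

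A simulation of 200,000 participants gave 2.75, 2.00 and 0.75.

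**Net effect when all visits are attended.** Recalled time is always 3 × 26 = 78 weeks. Actual follow-up is 78 + c = 75 to 81 weeks. The net mismatch is at most 3 weeks, and 3/78 = 3.8%. For example, late/early/late visits (29, 49 and 81 weeks) give:
- unasked: 3 + 0 + 6 = 9 weeks;
- double counted: 6 weeks;
- net: 9 − 6 = 3 weeks.

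**Effect on the expected 18-month total.**
- Constant event rate: 78 recalled weeks against 78 target weeks, so 0% bias.
- Event rate falling linearly to half by week 78 (assumption): expected true total 78 − 0.5 × 78/2 = 58.5 in units of the starting rate. With all visits three weeks late, weeks 3 to 81 are recalled and the expected count is 57.0; 57.0/58.5 − 1 = −2.6%. With all visits three weeks early the error is +2.5%. Averaged over uniform visit times it is about 0%.

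**An intermittent missed visit.**
- 6-month visit missed, 12-month attended: unasked time = 52 + b − 26 = 23 to 29 weeks.
- 12-month visit missed, 18-month attended: unasked time = (78 + c) − (26 + a) − 26 = 20 to 32 weeks.
- On nominal timing both are 26 weeks, and 26/78 = 33% of follow-up.

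**With recall running from the last completed assessment.** Unasked, double-counted and pre-baseline weeks are all 0 for every visit pattern up to the last visit attended. Time covered becomes 75 to 81 weeks for anyone who attends the 18-month visit.

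**The case against.** A reader might infer that the 18-month cost total is wrong, or that the comparison of arms is biased. The documents do not support either. With complete visits, gaps and overlaps largely offset one another, and the remaining noise falls on both arms alike. A bias between arms would need missed visits that differ by arm, or visit timing that differs by arm together with event rates that change over time. The documents give no data on these. Nor should the late/early/late pattern be read as a 15-week error: 9 + 6 adds errors of opposite sign.

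The plan also has partial safeguards:
- **Missing data.** Section 9.3 plans multiple imputation for missing visits and dropouts, and Section 9.6 plans inverse probability weighting for dropout. It would be unfair to say that a missed visit is simply summed as zero. But neither section says how its method applies to a partly observed cost total, and neither recovers events that a returning participant could report.
- **Administrative data.** Reimbursement data can calibrate self-report where the two overlap. They help only in part, because Section 9.6 still builds the total from self-report.
- **Other capture.** The medical history item in Section 6.2 collects physician visits, ER visits and hospitalizations at each assessment, and hospitalization is a serious adverse event under Section 7.3. Section 9.6 does not say that these feed the cost analysis.

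Two further points stand. The case report forms are not in the documents and may already carry a start date or event dates. A fixed recall also has merit: equal exposure at each visit, and the same period as at baseline.

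**Conclusion.** The mismatch is real but modest when all visits are attended: on average about 2.8 weeks unasked, 2.0 double counted and 0.75 before baseline per participant under uniform visit times, with a net error of at most 3 weeks (3.8%). This is mainly patient-level error in cost and event counts.

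The more important part is the intermittent missed visit, which leaves about a third of follow-up unasked of someone who is seen again. How many participants this affects cannot be judged from the documents. They give only an expected loss of up to 15% by 18 months, and permanent dropout is a separate problem that a change of recall wording does not solve.

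The conclusion takes six months as 26 weeks and the recall wording of Sections 6.2 and 9.5.2 as what the forms ask. It concerns the secondary cost and exacerbation outcomes only. The ACQ has a one-week recall and is untouched.

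**What to change.** On the follow-up utilization and exacerbation form:

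1. Replace the six-month look-back with *since your last completed assessment on [date]*, with the date pre-filled from REDCap. Keep the six-month look-back at baseline.
2. Record the month or date of each event, and exclude events before the baseline date.
3. State in Section 9.6 that counts and costs are analysed over the time actually covered, scaled or truncated to 18 months.
4. State in Section 9.6 that imputation and weighting apply only to time that remains unobserved.

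The cost is a change of form wording, one pre-filled field and a few lines in Section 9.6. The disadvantage is a longer recall after a missed visit: about 12 months (46 to 58 weeks with the windows), or longer if two visits are missed. That recall is less reliable, but the alternative is no report for the skipped period.

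A reader might want the same change for missed work or school ("Self-report of number of days of work or school missed because of asthma in the 6 months prior to each assessment"), the Confounding Effects Inventory and the CAM form. That is optional: Section 6.2 lists them as moderating or process variables, and Section 9.6 does not name them in the cost total.
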